A Pilot Peer Mentor Intervention That Trains Black Men Who Have Sex With Men (BMSM) to Use and Promote Uptake of HIV/STI Self-Testing to Peers and Sex Partners: STAR Study (Self-Testing at Your Residence)

NCT04121962

1/26/2021

JHSPH IRB Research Plan for New Data Collection

Use this template for new data collection and if you also will analyze secondary data. Answer the questions below and for numbered sections that do not pertain to your study, retain the section numbers and bolded questions, and write "N/A". Please start typing in the gray boxes provided.

PI Name: [name]

Study Title: A pilot Peer Mentor intervention that trains Black MSM to use and promote uptake of HIV/STI self-testing to peers and sex partners: STAR study (Self testing at your residence)

IRB No.: 9216

PI Version No. / Date: Version 6– 1-26-2021

I. Aims of the Study: Describe the aims/objectives of the research and/or the project's research questions or hypotheses.

The objectives of the study are to assess the feasibility, reach and preliminary efficacy of a brief intervention that trains Black men who have sex with men [referred to as Index] (a) to use home-based testing for HIV and sexually transmitted infections and (b) promote home-based testing to their peers and sexual partners. The study will be conducted in two phases: Component Testing and Pilot Trial. We have completed the phase to test the website components and refine the intervention content. We are now requesting permission to conduct the Pilot Trial.

The overall aims of the study are:

- 1) To examine feasibility of the Peer Mentor intervention to train BMSM to use and promote to peers and sex partners home-based HIV and STI self-testing kits. Measures include: session attendance, facilitators and barriers to outreach, fidelity to PEER communication tool.
- 2) To examine the reach of the intervention compared to a control condition (use of the self-testing website only). Measures include: number of peers and sex partners who use the website, characteristics of peers and sex partners (including sexual risk and HIV/STI testing history).
- 3) To determine preliminary effect sizes of the intervention on self-testing uptake. We expect that a greater proportion of BMSM and their peers and sex partners in the Peer Mentor condition will request test kits, return specimens for STI testing, and receive results compared to those in the control condition.

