Index will complete study visits (baseline, randomization session, 5 individual sessions (if randomized to experimental condition), 3 month follow-up) at the Lighthouse Studies @ Peer Point community-based research clinic.

Enrolled network members will complete baseline and 3 months follow-up study activities exclusively on-line via the Star website.

Both Index (in both conditions) and Networks will have access to home-based HIV testing and specimen collection for gonorhea and chlamydia testing via the Star website.

The experimental condition is a five session individual-based intervention that will train Index to be peer mentors and promote home-based testing.

The control condition is one individual-based session that will review information about HIV and STIs, home-based testing methods and how to use the website.

B. Provide a sample size and a justification as to how you arrived at that number. If you use screening procedures to arrive at a final sample a table may be helpful.

Component testing phase: We plan to conduct the component testing with up to 20 participants who will be split into two groups. We will hold one group and make revisions based upon this group's feedback then conduct the second group with the revised materials.

Full Trial: Index participants: We plan to enroll n=140 Index participants.

Network participants: Each Index will be able to recruit up to six Network participants - therefore up to 720 Networks may enroll. Based on estimates from one study of self-testing among MSM with option to refer peers (but were provided no training), we expect the average number of Index coupons distributed to the self-testing website will be up to 6 peers/partners and that of these 70% of the peers/partners referred will request a self-test kit. For experimental condition this

results in (n=265) kits requested by peers/partners and (n=143) kits requested by control condition peers/partners.

IV. Participants:

Describe the study participants and the population from which they will be drawn. Specify the inclusion and exclusion criteria. If you plan to include children, note their ages and whether you will include children in foster care. Note if the participants are particularly vulnerable in terms of cognitive limitations, education, legal migration status, incarceration, poverty, or some combination of factors.

Component testing phase: The study participants will be Black men who have sex with men.

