Aim 2: We will compare the reach of the two conditions in terms of (i) the number of peers recruited to access the self-testing website; and (ii) the characteristics of those recruited including sexual risk behavior, HIV/STI testing behavior, linkage to HIV/STI care, PrEP awareness and self-testing-related perceived norms. For the first part, as the number of peers/sex partners recruited by a mentor is a count, we will fit a model with log link with intervention condition as the only predictor to estimate the treatment-to-control ratio of mean number of peers recruited. For the second part, as the peers are clustered in the mentors who recruited them, we will use general estimating equations (GEE, which allow correlation among clustered units) to estimate treatment-control contrasts in each characteristic. We will include sex as a biologic variable in these analyses.

Aim 3: We will test and estimate differences (i) between intervention and control mentors and (ii) between intervention and control recruited peers in terms of: request of self-testing kits, return of specimens for STI testing, accessing of STI test results, and posting of HIV oral test result (all binary variables). For the mentors, we will use tests of two sample proportions and simple logistic regression with the intervention condition as predictor. For the peers, we will fit GEE logistic models to allow for correlation of outcome among clustered peers and will include sex as a biologic variable.

Secondary Analysis

Changes in knowledge and self-efficacy: We will examine the changes in the continuous measure of Knowledge score using linear regression adjusting for baseline knowledge score and other covariates. We will examine changes in self-efficacy by using a Chi-square test for a difference between two proportions of efficacy score.

Reasons for testing and future preferences: We will tabulate participant responses and compare proportions by condition using Chi-square tests.

5. Answer the following if they are relevant to your study design:

A. If the study has different arms, explain the process for assigning participants (intervention/control, case/control), including the sequence and timing of the assignment.

Component Testing: N/A

Full Trial:

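### Aim 3(ii) compares peer testing only as proportions among peers recruited after randomisation; no planned analysis gives a test or interval for peer testing per randomised Index

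*Combined protocol and SAP*

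**What the plan says.** Section I gives the purpose of Aim 3 as "To determine preliminary effect sizes of the intervention on self-testing uptake" and expects that "a greater proportion of BMSM and their peers and sex partners in the Peer Mentor condition will request test kits" and complete the later steps.

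Section V.C.4 (Full Trial, Aim 3) takes four binary outcomes: kit request, specimen return, access to STI results and posting of the HIV oral test result. Part (i) compares the Index themselves. Part (ii) compares "between intervention and control recruited peers in terms of: request of self-testing kits, return of specimens for STI testing" and the other two steps. For this, "we will fit GEE logistic models to allow for correlation of outcome among clustered peers", with sex included.

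Two other analyses in V.C.4 concern the network:

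- Aim 2(i) fits a log-link count model with condition as the only predictor, "to estimate the treatment-to-control ratio of mean number of peers recruited".
- Aim 2(ii) uses GEE to contrast recruited peers by arm on sexual risk, testing behaviour, linkage to care, PrEP awareness and perceived norms.

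Section V.C.5.A says that network members are not randomised and take the arm of the Index who invited them. Section V.C.1 has control Index receive their six invitations at the end of their session, which follows randomisation.

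Section III.B says "Each Index will be able to recruit up to six Network participants", assumes that "70% of the peers/partners referred will request a self-test kit", and concludes for the experimental arm that this "results in (n=265) kits requested by peers/partners and (n=143) kits requested by control condition peers/partners".

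**The concern.** The denominator of Aim 3(ii) is formed after randomisation, by the behaviour that the intervention trains. The experimental arm may recruit more peers, or different peers, so the two groups of recruited peers need not be comparable. GEE deals with correlation within an Index's network. It does not deal with this selection, and neither does adding sex. An Index who recruits nobody is not represented.

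If the intervention works mainly by bringing in more peers, the proportion among those recruited need not move, even though more peers are tested. Aim 2(i) would show the extra recruitment but stops at access to the website. A point estimate of peer kits per Index could be put together from the data behind Aims 2(i) and 3(ii), but it would have no definition, test or interval fixed in advance. Section III.B nevertheless expresses the expected network benefit as peer kits by arm, which no planned analysis compares.

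**Working it through.** **Inputs.** From Section III.B: 140 Index, up to six peers per Index, 70% of referred peers requesting a kit, and 265 v 143 peer kits. The allocation ratio is not stated, so 70 per arm is an assumption, as is one kit request per peer.

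**Reproducing the plan's totals.** Kits = Index per arm × peers per Index × 0.70.

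- 70 × 6 × 0.70 = 294, which is not 265. 63 × 6 × 0.70 = 264.6 does match, but needs an unstated 10% loss from 70.
- 143 cannot be reached with six peers at these arm sizes. 68 × 3 × 0.70 and 51 × 4 × 0.70 both give 142.8, but neither pair of inputs is stated.

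So the per-arm inputs behind 265 and 143 are unknown. The point about what is estimated does not depend on them.

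**Per-Index ratio.** 265/70 = 3.79 and 143/70 = 2.04; ratio 265/143 = 1.85. The ratio is the same at any equal arm size.

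**Aim 3(ii) if 70% applies in both arms.** Referred peers would be 265/0.70 = 378.6 and 143/0.70 = 204.3. Let e be the share of referred peers who enrol, the same in both arms and including everyone who requests a kit. The proportion requesting among recruited peers is 0.70/e in both arms, so the odds ratio is 1.00 for any e above 0.70. At e = 0.70 both proportions are 100% and the odds ratio is undefined.

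**Another split of the same totals.** If every Index in both arms recruited six, all of whom enrolled, the proportions would be 265/420 = 63.1% and 143/420 = 34.0%. The odds ratio is (265/155)/(143/277) = 3.31, and Aim 2(i) would show no difference. Neither proportion is 70%, but the documents do not settle which split was meant.

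**Can the odds ratio reverse?** Suppose control refers 204.3/70 = 2.92 peers per Index at 70%. Suppose experimental refers the same 2.92 at 70% plus 378.6/70 − 2.92 = 2.49 extra peers at an assumed 50%.

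- Experimental kits per referred peer: (2.92 × 0.70 + 2.49 × 0.50)/5.41 = 60.8%.
- Kits per Index still rise by 61% (ratio 1.61).
- With full enrolment, the odds ratio is (0.608/0.392)/(0.70/0.30) = 0.66. With 80% enrolment for all peers, it is 76.0% v 87.5%, or 0.45.
- If the extra peers instead enrol less often in proportion to their lower interest (0.80 × 50/70 = 57.1%), their proportion is 0.50/0.571 = 87.5%. That equals control's 0.70/0.80, and the odds ratio returns to 1.00.

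**Precision of the added ratio, 70 per arm.** A count between 0 and 6 with mean m has variance at most m(6 − m). So the SE of the log ratio is at most √{[(6 − 3.79)/3.79 + (6 − 2.04)/2.04]/70} = 0.190.

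| Means | Largest SE, 95% CI | Poisson SE, 95% CI |
|---|---|---|
| 3.79 v 2.04 | 0.190, 1.28–2.69 | 0.104, 1.51–2.27 |
| 1.85 v 1.0 (assumed) | 0.322, 0.99–3.48 | 0.148, 1.39–2.48 |

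**The case against.** The plan answers the question that it asks. Section I words the Aim 3 hypothesis as a proportion and gives reach to Aim 2. Reach per Index plus uptake among those reached is a coherent division. Section V.C.5.A discloses that network members are not randomised, and Aim 2(ii) looks directly at who was recruited in each arm. This is a pilot seeking preliminary effect sizes, in a template that asks for a brief analysis plan.

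Most of this stands. Aim 3(ii) does not conflict with its hypothesis and should be kept. Aim 2(ii) is a useful check on selection, although comparing characteristics shows imbalance without removing it. What remains is that the plan never links the disclosed structure to the reading of Aim 3(ii), and that peer testing per randomised Index has no pre-specified estimate.

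A reader might also infer that Aim 3(ii) is bound to show no effect, or to favour control. The documents do not support that. The null result needs the same 70% in both arms. Section I expects a higher proportion in the Peer Mentor arm, and the 70% in Section III.B comes from a study whose referrers had no training. The reversal needs assumed request rates and also equal enrolment of the less interested peers; with proportionally lower enrolment it disappears.

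**Conclusion.** The point holds as a gap, and closing it is a cheap improvement. The peer contrast in Aim 3(ii) is conditional on recruitment after randomisation, and none of Aims 2(i), 2(ii), 3(i) or the secondary analyses supplies a test or interval for peer testing per randomised Index.

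The gap is clear from the text alone. Its size is not. A 1.85-fold difference in peer kits per Index could sit beside an Aim 3(ii) odds ratio of 1.00 under a common 70%, or beside one well above 1 under another split. The 1.85 rests on equal allocation, one request per peer and totals that cannot be rebuilt from the stated inputs.

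**What to change.** Keep the Aim 3(ii) GEE analysis with sex, label it a non-randomised comparison, and read it beside Aim 2(ii).

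Add four Index-level counts over all randomised Index, by allocated arm, with zeros kept: network members who request a kit, return specimens, view STI results and post an HIV result. For each, estimate the treatment-to-control ratio of means with a 95% CI from the Aim 2(i) log-link model with robust variance.

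State one counting rule in advance. Count peers who enrol within a fixed window from the Index's randomisation date, the same in both arms, and follow each for 3 months from their own enrolment (the network duration in Section V.C.3). The window must cover the five weekly sessions and the 30 day check-in. That is about 28 + 30 = 58 days from the first session if the check-in is timed from the fifth, which the plan does not state, plus any wait before the first session.

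A clock tied to the last session belongs only in a sensitivity check. That date arises after randomisation, differs by arm and is undefined for an Index who attends nothing. It would either drop early recruits or give the experimental arm longer to accrue them.

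The cost is plan text and one rule. StarCodes already link peers to Index (Section V.A.1), the website records the date of network consent (Section V.B.1.i), and Aim 3 already uses the four outcomes. There are three downsides:

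- The ratio combines reach and uptake, so it must be reported beside the Aim 2(i) count and the peer proportion.
- A randomisation clock leaves the experimental arm less time after training ends.
- Precision may be modest, and at a low control mean the interval could include 1.

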At the end of Session 1, the facilitator will explore potential facilitators and barriers of utilizing the self-testing website (such as, "How would you describe your experience with setting up an account, requesting kits, and viewing results? What would you change about the website?"). Participants will also be shown different designs for the coupons to be used to refer peers and sex partners to the website and asked about acceptability of the coupon design. Finally, participants will be asked to spend time over the next week engaging in conversations with their peers and/or sex partners about the referral coupons and website and potential challenges or concerns about being referred to the website. The peers won't be asked to log-onto the website and create an account (because the website will not yet be "live",) but the Peer Mentor will have screen shots of different pages of the site to show their peers. The session will be audio-recorded and observed by the study PI who will take notes with a focus on suggestions for revisions to the intervention materials and website and use these results to refine the materials.

Session 2: Participants will be asked to share the results of their conversations with peers/sex partners, such as challenges to having the conversation, concerns of the peers/sex partners and reactions/suggestions to the referral coupon and screenshots. The session will be audio-recorded and observed by the study PI who will take notes with a focus on suggestions for revisions to the intervention and website. These results will also be used to refine the materials.

Results of the Component Testing: 12 participants completed the component testing phase.

Suggestions to change the website included: increase amount of information about STIs and how the testing works, add more visuals such as pictures. Participants were enthusiastic about the concept of being able to self-test at home and share this resources with peers and sex partners.

Full Pilot Trial: This will be a randomized controlled trial with data collection at baseline and 3 month follow-up. There will be two types of participants in the trial: Index and Network. Index will be Black men who have sex with men (BMSM) who will be randomized to the experimental arm or control arm. Index in both arms will be asked to recruit individuals from their personal social networks to enroll in the study via the study web-site (see mock-ups of Star website).

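### The Index comparisons in Aims 2(i) and 3(i) use no baseline covariate; they are valid as planned, but some precision may be lost and could be recovered at little cost

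*Combined protocol and SAP*

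**What the plan says.** All of the analysis wording is in section V.C.4.

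- **Aim 2(i), number of peers recruited by each Index:** "we will fit a model with log link with intervention condition as the only predictor".
- **Aim 3(i), four binary Index outcomes:** tests of two sample proportions and "simple logistic regression with the intervention condition as predictor".
- **Peer-level models (Aims 2(ii) and 3(ii)):** for the recruited peers the plan uses GEE and "will include sex as a biologic variable". These are not Index outcomes and lie outside this point.
- **Secondary analysis of the knowledge score:** "linear regression adjusting for baseline knowledge score and other covariates". The other covariates are not named.

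On design, section III.A states "This will be a randomized controlled trial with data collection at baseline and 3 month follow-up". Section V.C.1 places randomisation after the baseline survey. Section V.C.5.A describes a sequence prepared in advance by the Data Manager and mentions no stratification factor. On size, section III.B states "We plan to enroll n=140 Index participants".

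**The concern.** Data collected before randomisation are used for a secondary outcome but not for the Index outcomes that carry Aims 2(i) and 3(i), and no reason is given. Section I sets Aim 3 the task of producing preliminary effect sizes, so the width of the interval around each estimate largely determines how useful the result is. With 140 Index and no stated stratification, the arms may differ by chance on factors that predict uptake. Adjusting for such a factor removes the part of the noise that it explains.

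What is at stake is the standard error of the preliminary estimates, not their validity.

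**Working it through.** **Inputs from the documents.** 140 Index (section III.B); arm-only models for Index (V.C.4); baseline survey before randomisation (V.C.1).

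**Assumptions, because the documents give no figure.** 1:1 allocation, so 70 per arm; no dropout; outcome near 50%; one binary baseline factor held by half of Index (f = 0.5) that shifts the outcome by d = 20 to 40 points.

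**The plan's own figure.** The 140 comes with no alpha, power, event rate or effect size for the Index comparisons, so it cannot be reproduced. Nothing below changes it.

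**Step 1, unadjusted standard error of the risk difference.** SE = sqrt(2 × 0.25/70) = 0.0845, or 8.45 points.

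**Step 2, share of outcome variance explained.** R² = f(1−f)d² / [p(1−p)] = 0.25d²/0.25 = d².

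**Step 3, adjusted SE and equivalent gain in participants.** SE × sqrt(1−R²), and 1/(1−R²) − 1.

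| Shift d | R² | Adjusted SE (points) | Fall in SE | Equivalent extra participants |
|---|---|---|---|---|
| 0 | 0 | 8.45 | 0% | 0% |
| 20 points | 0.04 | 8.28 | 2.0% | 4% |
| 30 points | 0.09 | 8.06 | 4.6% | 10% |
| 40 points | 0.16 | 7.75 | 8.3% | 19% |

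**Step 4, chance imbalance.** The between-arm difference in the factor also has SD sqrt(2 × 0.25/70) = 8.45 points. A typical 1-SD imbalance moves the unadjusted estimate by 8.45 × 0.20 to 8.45 × 0.40, that is 1.7 to 3.4 points. A 1.96-SD imbalance (16.6 points) moves it by 3.3 to 6.6 points, but an imbalance that large arises in about 5% of trials. Neither adds to step 3. The squared 1-SD shift over the squared SE is 1.69²/8.45² = 0.04 and 3.38²/8.45² = 0.16, which are the same R² values.

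**Step 5, simulation of the binary outcomes** (70 per arm, one continuous covariate, 3,000 runs).

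| R² | SD of risk difference, unadjusted | SD, standardised after adjustment | Mean log odds ratio, unadjusted → adjusted | Its SE, unadjusted → adjusted |
|---|---|---|---|---|
| about 0 | 0.0822 | 0.0824 | 0.82 → 0.83 | 0.348 → 0.351 |
| 0.11 | 0.0845 | 0.0806 | 0.74 → 0.84 | 0.347 → 0.374 |
| 0.17 | 0.0824 | 0.0752 | 0.70 → 0.85 | 0.346 → 0.388 |

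The SD of the risk difference falls by about 5% and 9% in the last two rows, while the odds ratio moves to a conditional value with a larger SE. The reporting scale therefore matters.

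**Step 6, cost of uninformative covariates.** A second simulation (40% versus 60%, 6,000 runs) adjusted for three covariates, of which at most one was prognostic. The ratio of adjusted to unadjusted SD was 1.013, 1.006, 0.990, 0.958 and 0.927 for a factor worth 0, 10, 20, 30 and 40 points.

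**Step 7, count outcome** (log link, counts capped at 6, robust SE, 2,000 runs). At R² of about 0.14 the SD of the log ratio fell from 0.139 to 0.132 and power rose from 71% to 77%; the mean log ratio stayed at 0.34. With no prognostic value the SD was 0.130 unadjusted and 0.132 adjusted.

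**The case against.** The strongest reply is that nothing here is wrong. Randomisation makes the unadjusted comparison valid, no stratification factor is stated that would require adjustment, the form asks only for a brief analysis plan, and raw proportions by arm are directly usable from a pilot. All of that stands.

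Four stronger readings are tempting, and the documents do not support them.

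- **That the plan contradicts itself by adjusting knowledge and not uptake.** The knowledge score has its own baseline value. Section V.C.1 describes website access for randomised Index, so kit request, specimen return, result access and peers recruited have no pre-randomisation value. Only proxies are available.
- **That precision is certainly being given away.** No document says how strongly any baseline item predicts uptake or recruitment. The natural candidate, testing history, is listed for recruited peers and partners (Aim 2 in sections I and V.C.4), but the Index survey items are not listed. What is documented is a baseline knowledge score (V.C.4, which does not name the participant group; I read it as including Index) and age, an eligibility item (IV.A).
- **That a damaging imbalance is likely.** The large shift is a 5% event, and the unadjusted standard error already allows for it.
- **That adjustment cannot introduce bias.** The standardised estimate is consistent in large samples. With 140 Index and outcomes of unknown frequency, a logistic model with several covariates can meet sparse cells.

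A further objection is that adjustment changes what the odds ratio estimates. It does, as step 5 shows. A standardised risk difference avoids this, because it targets the same quantity as the planned comparison of two proportions.

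**Conclusion.** The point holds as an optional efficiency improvement, not as an error. The Index analyses in Aims 2(i) and 3(i) ignore baseline information collected before randomisation. Under the stated assumptions, a factor worth 20 to 40 points lowers the SE from 8.5 to between 8.3 and 7.7 points. The upper end needs a strong predictor, and the documents do not show that one is measured in Index. If the covariates are not prognostic, the gain is nil or about 1% of precision is lost. For the count outcome the gain is similarly modest and rests on simulation alone, since nothing in the documents links a baseline item to the number of peers recruited.

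**What to change.** In section V.C.4, for the Aim 3 Index outcomes, prespecify a logistic model on arm plus one or two baseline covariates: baseline knowledge score and age. If the Index baseline survey records recent HIV/STI testing, use that in place of one of them. Report the standardised risk difference with a robust standard error. Add the same covariates to the Aim 2(i) log-link model. Name the covariates before outcomes are examined by arm, so that the choice cannot follow the results.

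Keep the unadjusted proportions and the unadjusted ratio alongside, and state that they become the reported result if an outcome is too sparse for the adjusted model to fit.

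The cost is a few lines of analysis wording and slightly more analysis work. No new data are needed, since testing history is used only if it is already collected. The downside is the possible loss of about 1% of precision if the covariates prove uninformative.

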Index: After completing the baseline visit, Index will be informed about the time and date for session 1 of the two different arms (e.g. randomization). Index will be randomized to condition in the order that they arrive on randomization. The study will use a pre-determined randomization sequence that was generated by the Data Manager.

Network: Do not attend randomization. Their assignment to condition is based on the assignment of the Index who invited them to the study.

B. If human biospecimens (blood, urine, saliva, etc.) will be collected, provide details about who will collect the specimen, the volume (ml) and frequency of collection, how the specimen will be used, stored, identified, and disposed of when the study is over. If specimens will be collected for use in future research (beyond this study), complete the “Biospecimen Repository” section below.

Component testing: N/A

Full Trial:

Index: See Biospecimen table

Network: See Biospecimen table

C. If genetic/genomic analyses are planned, address whether the data will be contributed to a GWAS or other large dataset. Address returning unanticipated incidental genetic findings to study participants.

N/A

D. If clinical or laboratory work will be performed at JHU/JHH, provide the JH Biosafety Registration Number.

Component Testing: N/A

Full Trial: The laboratory is CLIA-certified (CLIA # 21D0680509) and undergoes a biennial accreditation inspection administered by the College of American Pathologists (CAP # 1353001). The laboratory is also licensed by the State of Maryland (Permit # 008).

E. If you will perform investigational or standard diagnostic laboratory tests using human samples or data, clarify whether the tests are validated and/or the lab is certified (for example is CLIA certified in the U.S.). Explain the failure rate and under what circumstances you will repeat a test. For all human testing (biomedical, psychological, educational, etc.), clarify your plans for reporting test results to participants and/or to their families or clinicians. Address returning unanticipated incidental findings to study participants.

N/A

F. If your study involves medical, pharmaceutical or other therapeutic intervention, provide the following information:

a. Will the study staff be blind to participant intervention status?

Component testing: N/A

Full Trial:

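### Change in self-efficacy is tested by a Chi-square on two undefined proportions; baseline-adjusted regression, already planned for knowledge, would be more precise at almost no cost

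*Combined protocol and SAP*

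**What the plan says.** Section V.C.4, Full Trial, Secondary Analysis, treats two measures under one sub-heading about changes in knowledge and self-efficacy. For knowledge: "We will examine the changes in the continuous measure of Knowledge score using linear regression adjusting for baseline knowledge score and other covariates". For self-efficacy, in the next sentence: "We will examine changes in self-efficacy by using a Chi-square test for a difference between two proportions of efficacy score".

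Self-efficacy appears nowhere else in the documents. No instrument, score range, threshold or definition of change is given. The item that follows, on reasons for testing and future preferences, says that its Chi-square tests compare the conditions; the self-efficacy sentence does not say so.

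The design supplies both time points. Section III.A says: "This will be a randomized controlled trial with data collection at baseline and 3 month follow-up". Section III.B gives the number: "We plan to enroll n=140 Index participants". Section V.C.5.A describes allocation without a ratio: "The study will use a pre-determined randomization sequence that was generated by the Data Manager".

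**The concern.** A score has no proportions until someone fixes a cut or names a category, and the plan does neither. The stated purpose is to examine change, yet a Chi-square test on two proportions has no term for a baseline value. Baseline can enter only if it is built into the outcome, for example as improved or not improved.

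The team adjusts for baseline one sentence earlier, so its own method and the planned data collections already allow a better analysis. At stake is the information that a pilot with 140 Index participants can extract on this one secondary outcome, and whether a later trial inherits a usable effect estimate with an interval.

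**Working it through.** The documents contain no figure for self-efficacy (no effect size, SD, event rate, cut or power), so there is nothing to reproduce. What follows compares the possible readings of the sentence.

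**Inputs**
- From the documents: 140 Index participants (III.B); measurement at baseline and 3 months (III.A); a Chi-square test on two proportions (V.C.4).
- Assumed: 1:1 allocation, so 140/2 = 70 per arm with no dropout; baseline to 3-month correlation r = 0.3, 0.5 or 0.7; a normally distributed score where the measure is graded; two-sided alpha 0.05.

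The comparator is a regression of the 3-month value on condition and baseline. Its residual variance is (1 − r²) times the unadjusted variance.

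**Reading 1: graded measure, 3-month level split at the median, compared by arm.** A median split keeps 2/π = 0.637 of the efficiency of the unadjusted comparison of means. Relative to the adjusted model this becomes (2/π)(1 − r²).

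**Reading 2: graded measure, proportion improved, compared by arm.** The change score has variance 2(1 − r), so its efficiency relative to the adjusted model is (1 − r²)/[2(1 − r)] = (1 + r)/2. Reducing it to improved or not costs a further 2/π, giving (2/π)(1 + r)/2.

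**Reading 3: binary measure, 3-month proportions compared by arm.** There is no splitting loss. Let φ be the baseline to 3-month correlation of the binary values. For a median cut of an underlying normal score, φ = (2/π)·arcsin(r) = 0.194, 0.333, 0.494. Efficiency without baseline is 1 − φ².

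| Efficiency kept | r = 0.3 | r = 0.5 | r = 0.7 |
|---|---|---|---|
| 1. Split 3-month level | 0.637 × 0.91 = 0.579 | 0.637 × 0.75 = 0.477 | 0.637 × 0.51 = 0.325 |
| 2. Proportion improved | 0.637 × 0.65 = 0.41 | 0.637 × 0.75 = 0.48 | 0.637 × 0.85 = 0.54 |
| 3. Binary, no baseline term | 1 − 0.194² = 0.962 | 1 − 0.333² = 0.889 | 1 − 0.494² = 0.756 |

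Reading 3 is thus a loss of about 4%, 11% or 24%. A simulation under no effect (4,000 runs; 63 per arm, an assumed size that is not in the documents; risk difference standardised from a logistic model with binary baseline) gave adjusted-to-unadjusted variance ratios of 0.974, 0.895 and 0.751, in line with the formula.

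**Reading 4: baseline and 3-month proportions in the same people.** The ordinary Chi-square assumes independent groups, so it ignores the pairing. It also contains no contrast between the arms, so an efficiency ratio does not apply.

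**What Reading 1 means for power.** Take a standardised effect of 0.5, which is also assumed. With the cut at the control median, the proportions above it are 0.500 and 0.691. With 70 per arm the Chi-square test has power 0.639. The adjusted regression has standard error √[2(1 − r²)/70] in SD units and power 0.873, 0.927 or 0.985 at r = 0.3, 0.5 or 0.7. For 80% power the split needs 102 per arm, against 58, 48 or 33. The ratios 58/102 = 0.57, 48/102 = 0.47 and 33/102 = 0.32 agree with the first row of the table.

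**The case against.** The best defence is that the sentence answers a form item asking for a brief analysis plan, that only knowledge is called continuous, and that the method may simply have been matched to the type of measure. Self-efficacy may be binary or coarse, and then a test of proportions is an ordinary choice. It would also match Aim 3, where the plan says: "For the mentors, we will use tests of two sample proportions and simple logistic regression with the intervention condition as predictor". Much of this stands. The different treatment of the two measures is not in itself an error, and the larger losses apply only if the measure is graded. It does not remove the point, because the adjusted model is more efficient on each between-arm reading examined, the binary one included.

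A reader might infer four stronger things that the documents do not support.

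- *Baseline is certainly ignored.* The sentence speaks of changes, so it may mean the proportion improved, with baseline inside the outcome. Reading 2 covers that case.
- *The comparison is biased.* Between randomised arms in Index participants, with a cut fixed in advance, the Chi-square test is valid. The issue there is precision.
- *Clustering is mishandled.* Network members are also followed: "Enrolled network members will complete baseline and 3 months follow-up study activities exclusively on-line via the Star website". But nothing says this test includes them. Where Aim 3 analyses peers, "we will fit GEE logistic models to allow for correlation of outcome among clustered peers"; the peer characteristics listed under Aim 2 do not include self-efficacy; and the peer-mentor training goes to Index participants only.
- *The false-positive rate will be inflated.* Taking the best of three or five candidate cuts would raise a 5% error rate to about 12.7% or 17.0% (simulation, 40,000 runs, 70 per arm). The plan does not say that the cut will be chosen after the data are seen; it is silent. This is a reason to fix any cut in advance, not a finding about the trial.

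**Conclusion.** The point holds as a minor, nearly free improvement. The plan leaves the two proportions and their cut undefined, and it uses a test that is less efficient than the baseline-adjusted approach it already applies to knowledge.

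How large the loss is depends on facts that the documents do not give. It is roughly half or more of the efficiency in most of the graded cases examined and 4% to 24% if the measure is binary. These figures rest on the assumed normal score, median cut, 1:1 arms and range of r, and should be read as illustrations. Only on the time-point reading is the difficulty more than precision, because the test would then not address the effect of the intervention; the text does not show that this reading is intended.

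The sample size and Aims 1 to 3 do not depend on this analysis.

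**What to change.** Replace the self-efficacy sentence with one along these lines: in Index participants, 3-month self-efficacy will be regressed on condition, adjusted for baseline self-efficacy, using a linear or proportional-odds model if the measure is graded and a logistic model if it is binary; the adjusted effect will be reported with a 95% confidence interval. If the measure is binary, a standardised risk difference is a useful companion to the odds ratio, since it is the quantity to which the simulated precision gain refers. Show any split of a graded score descriptively only, with the cut fixed in advance.

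The cost is one or two sentences of plan text and a little analysis work. No new data are needed: examining change already requires self-efficacy at both time points, and both data collections are planned.
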